2.0 Scientific Endpoints

2.1 Describe the scientific endpoint(s), the main result or occurrence under study.

NOTE: Scientific endpoints are outcomes defined before the study begins to determine whether the objectives of the study have been met and to draw conclusions from the data. Include primary and secondary endpoints. Some example endpoints are: reduction of symptoms, improvement in quality of life, or survival. Your response should **not** be a date.

Response: **Primary endpoint:** Change from baseline in HbA1c at 26 weeks as compared to placebo. **Secondary endpoints:** Change from baseline as compared to placebo in a)fasting and postprandial blood sugars, mean weekly glucose concentrations, standard deviation of weekly blood sugars and fructosamine; b)fasting and postprandial glucagon and C-peptide concentrations; c)insulin doses; d)indices of oxidative and inflammatory stress in MNC, plasma and adipose tissue; e)oxidative and inflammatory stress in plasma

and MNC following meal challenge; f)subcutaneous fat mass, hepatic fat content and visceral fat mass; g)waist circumference, blood pressure, triglycerides, HDL cholesterol and incidence of metabolic syndrome; h)gastric emptying; i) 24 hour blood pressure; j) flow mediated dilatation in brachial artery, k) SF-36 score; l) depression (PHQ) score.

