10.0 Procedures Involved

10.1 Provide a description of **all research procedures or activities** being performed and when they are performed once a subject is screened and determined to be eligible. Provide as much detail as possible.

NOTE: This should serve as a blueprint for your study and include enough detail so that another investigator could pick up your protocol and replicate the research. For studies that have multiple or complex visits or procedures, consider the addition of a schedule of events table in in your response.

Response:

Screening Visit: Consent will be explained and signed. Fasting labs before 10:00am include; CBC, CMP, HbA1c, lipid panel, C-peptide and GAD-6 and a urine pregnancy test. Physician preformed physical and medical history, including; blood pressure, height and weight. Blood samples of patients with negative GAD-65 antibodies will be screened for islet cell antibodies, if patient had evidence of auto- immunity to beta cells in the past, they will be retested during screening. Patients with no evidence of autoimmunity to beta cells will not be included in this trial.

Study Visit day -14: After screening visit, qualifying patients will see a registered dietitian who will review their carbohydrate counting and diet and make an assessment of their calorie and carbohydrate intake. Then they will be seen by a CDE for instructions on

injection technique and CGM insertion. The patients will be blinded to CGM. Patients who have been using CGM prior to enrolling in the study can continue to use their CGM's (unblinded). All subjects will be advised to monitor their capillary blood glucose by fingerstick before and 2 hours after each meal and to wear their CGM constantly for a week. The subjects will also be asked to keep a diary of their food intake for a week to measure their calorie intake. Study subjects will not change the type of glucose meter during the trial. They will have their body composition measured by DEXA and MRI prior to the next visit. Smoking patients will be asked not to change their smoking habits during the study.

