Study Visit day 0: Subjects will come fasting for this visit. Each subject will be given one injection of Liraglutide 1.2 mg or placebo. A fructosamine and blood samples will be collected at baseline. Blood samples will be collected after the baseline at 30, 60, 120, 180, 240 and 300 minutes after the injection. (**This is being done to evaluate the acute effect of a single injection of Liraglutide on oxidative stress and inflammatory mediators, before any adjustments of insulin dose or effect of Liraglutide on blood glucose and weight is evident**). Subjects will be instructed by the study staff in the dosing and administration of the study medication. They will start Liraglutide injection at a dose of 0.6 mg per day or placebo injection on the following day. We will adjust the doses of basal and bolus insulin to eliminate low blood sugars(less than 70 mg/dl). At all subsequent visits insulin doses will be titrated to target blood sugars between 70-180 mg/dl at all times. Patients will return to the center after 7 days.

Study Visit week 1: Blood glucose concentrations will be reviewed. Insulin dose will be adjusted at the discretion of the study investigator to optimize blood sugar control as per

the targets mentioned above. Patients will be advised to increase the Liraglutide dose to 1.2 mg a day if they are able to tolerate the 0.6 mg dose. If they are experiencing mild nausea, subjects will continue with 0.6 mg daily for another 7 days. Those with severe nausea/vomiting will be dropped from the study. All other subjects will return in 7 days.

Study Visit week 2: Blood glucose concentrations will be reviewed. Insulin dose will be adjusted if needed. Subjects taking 0.6 mg dose and experiencing significant nausea will be dropped from the study. Subjects on 1.2 mg and experiencing significant nausea will decrease the dose to 0.6 mg and continue that dose for the duration of the study. Subjects on 1.2mg and experiencing mild nausea will continue on 1.2 mg for 2 more weeks. Subjects on Liraglutide 1.2mg daily without any gastro-intestinal side-effects will be asked to increase the dose to 1.8 mg daily. Study drug will be dispensed for additional 2 weeks.

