Study Visit week 4: Subjects will be asked to bring in their used study pens and the pen that they are using so that study nurse can log in the amount of drug used. If needed, the dose will be increased. The goal in the first 4 weeks is to increase patient's liraglutide dose to maximum tolerated dose. Maximum dose of liraglutide will be 1.8 mg daily. Subjects experiencing mild nausea with 0.6 mg or 1.2 mg will continue at that dose in the study. Those with severe nausea/vomiting with 1.8mg will decrease their dose to 1.2 mg and continue that dose throughout the study. Blood glucose concentrations will be reviewed. Insulin dose will be adjusted if needed. CGM will be discontinued. Study drug will be dispensed to last till the next visit.

Study visit week 8: Subjects will be asked to bring in their used study pens and the pen that they are using so that study nurse can log in the amount of drug used. Blood glucose concentrations will be reviewed. Insulin dose will be adjusted if needed. Study drug will be dispensed to last till the next visit.

Study Visit week 12: Subjects will be asked to bring in their used study pens and the pen that they are using so that study nurse can log in the amount of drug used. Blood glucose concentrations will be reviewed and vascular activity will be performed. Insulin dose will be adjusted if needed. Fasting blood, research labs, HbA1c, fructosamine, lipid panel, urine pregnancy test and 24 hr urine will be collected. FMD and 24hr blood pressure will be studied. Study drug will be dispensed for additional 4 weeks.

Study Visit week 16 and 20: Subjects will be asked to bring in their used study pens and the pen that they are using so that study nurse can log in the amount of drug used. Blood glucose concentrations will be reviewed. Insulin dose will be adjusted if needed. Study drug will be dispensed for additional 4 weeks.

Study visit week 24: CGM will be inserted. They will have their body composition measured by DEXA and MRI prior to next visit.

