Study Visit week 26: Subjects will come fasting for this visit. Research labs, CBC, CMP, Lipids, HbA1c and fructosamine will be collected. Records of blood glucose concentrations monitored by finger-stick and CGM for the previous 14 days will be obtained to assess their glycemic control. They will undergo meal challenge test (described above) and a fat biopsy. 24 hr urine will be collected. FMD and 24hr blood pressure will be performed. After this visit, subjects will be discharged from the study.

Blood samples (collected in protease and DPP-IV inhibitors) will be appropriately processed and assayed for glucose, C-peptide, glucagon, GLP-1 and gastric inhibitory peptide (GIP) which is also called gastric insulinotropic peptide, Reactive oxygen species (ROS) generation, Thiobarbituric acid reducing substances (TBARS), urinary isoprostanate,

intranuclear nuclear factor kappa B (NFkB) binding, the expression and concentration of Toll like receptor-4 (TLR-4), tumor necrosis factor alpha (TNF α), Inhibitor kappa B (IkB α), Matrix metalloproteinase 9 (MMP-9), Suppressor of cytokine signaling-3 (SOCS-3), Protein kinase C (PKC β II), Phosphotyrosine phosphatase -1B (PTP-1B), Glycogen synthase kinase 3 beta (GSK-3 β), Inhibitor kappa kinase (IKK β), C-jun amino terminal kinase (JNK-1) and amount of Insulin receptor (IR- β) and p-IR β in MNC and plasma concentrations of C-reactive protein (CRP), Monocyte chemoattractant protein -1 (MCP-1), Plasminogen activator inhibitor -1 (PAI-1), TNF α and Regulated upon activation Normal T cell Expressed and Secreted (RANTES). Adipose tissue samples will be processed and analyzed for intranuclear NFkB binding, the expression and concentration of TLR-4, TNF α , IkB α , MMP-9, SOCS-3, PKC β II, PTP-1B, GSK-3 β , IKK β , JNK-1 and amount of IR- β and p-IR β .

Clinical and Laboratory Procedures

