17.0 Data Management and Analysis

17.1 Describe the data analysis plan, including any statistical procedures. This section applies to both quantitative and qualitative analysis.

Response: The focus of the proposed research is to evaluate the effect of liraglutide on mean HbA1c% over the period of 26 weeks of treatment. The similarities between the study groups, baseline values for subject's demographics and study endpoints will be compared using appropriate parametric tests. Transformations of the data in order to meet statistical assumptions may be considered. The **primary endpoint** of the study is to detect

a difference in HbA1c after 26 weeks of treatment with Liraglutide or placebo. The statistical analysis will be carried out using analysis of covariance (ANCOVA) and tested at the 0.05 level. Change in weight will be a covariate. The results will be computed as mean \pm SD. Analysis will be carried out on the basis of intention to treat (with last observation carried forward).

The secondary end points based on glycemic changes will include the difference from baseline in mean weekly glucose concentrations, standard deviations of the mean weekly glucose concentrations, HbA1c, fructosamine, the duration of time spent in hyperglycemia ($>150\text{mg/dl}$, $>200\text{mg/dl}$, $>250\text{mg/dl}$) and hypoglycemia ($<70\text{mg/dl}$, $<40\text{mg/dl}$), insulin dosage. A reduction in the AUC following the meal will constitute another secondary end point. Between groups comparisons of the magnitude of change from baseline will also be made for these glycemia related secondary endpoints using student's t-test. Comparisons for these and the primary endpoints will also be made using the paired t-test or Wilcoxon's test for paired data within each group.

The other secondary end-points of the study will be change from baseline after 26 weeks of treatment in the fasting and postprandial blood sugars, glucagon and C-peptide concentrations, indices of oxidative and inflammatory stress in MNC, plasma and adipose tissue; subcutaneous fat mass, hepatic fat content and visceral fat mass; features of metabolic syndrome; gastric emptying, blood pressure, vascular analysis, patient reported nausea, quality of life and depression scores. Between groups comparisons will be made using students t-test or ANCOVA (adjustment will be done for baseline differences). Within group comparisons for these endpoints will be made using paired t-test or Wilcoxon's test or ANCOVA.

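### Patients who leave before week 12 have no scheduled post-baseline HbA1c, so last observation carried forward scores them as exactly zero change, and the plan schedules no HbA1c that could test that zero

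*Combined protocol and SAP*

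**What the plan says.** The primary endpoint (section 2.1) is "Change from baseline in HbA1c at 26 weeks as compared to placebo".

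Section 10.1 lists HbA1c at three visits only:
- Screening: "Fasting labs before 10:00am include; CBC, CMP, HbA1c, lipid panel, C-peptide and GAD-6 and a urine pregnancy test". No later pre-treatment HbA1c is listed, so this is the baseline.
- Week 12: "Fasting blood, research labs, HbA1c, fructosamine, lipid panel, urine pregnancy test and 24 hr urine will be collected".
- Week 26: "Research labs, CBC, CMP, Lipids, HbA1c and fructosamine will be collected".

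The same section removes patients well before week 12. At week 1: "Those with severe nausea/vomiting will be dropped from the study". At week 2: "Subjects taking 0.6 mg dose and experiencing significant nausea will be dropped from the study".

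The only missing-data rule, in section 17.1, is "Analysis will be carried out on the basis of intention to treat (with last observation carried forward". It does not say what happens to a randomised patient with no post-baseline HbA1c, and no sensitivity analysis is described.

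Section 20.2 offers leavers an end-of-study visit only where needed and for safety; neither an HbA1c nor a date is attached to it. Section 20.3 uses data up to withdrawal. It promises further efficacy collection only to patients who skip some procedures but stay in the study. Section 10.4 names electronic medical records as a data source but does not commit to taking clinic HbA1c from them. Section 17.2 allows for 30% dropout.

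**The concern.** For a patient who leaves at week 1 or 2, or at any time before week 12, the last HbA1c is the screening value. Carried forward, it makes the change exactly zero by construction. Omitting such patients would avoid this but would not be intention to treat, and section 17.1 does not say which applies.

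Zero may be wrong for two linked reasons. Section 10.2 places nausea at the start of liraglutide and at dose escalation, so early loss may differ between arms. Insulin is also adjusted for everyone who keeps attending: "At all subsequent visits insulin doses will be titrated to target blood sugars between 70-180 mg/dl at all times". HbA1c may therefore move in both arms among those who stay, and leavers may or may not share that movement. If early loss is unequal and leavers do share it, a block of zeros in one arm distorts the treatment difference. This is the trial's single primary endpoint, and an HbA1c that nobody drew cannot be reconstructed at analysis.

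**Working it through.** **The plan's own figure.** Difference 0.35, SD 0.5, two-sided alpha 0.05 (sidedness assumed), power 80%: n per arm = 2 × (0.5 × (1.960 + 0.842) / 0.35)² = 32.04, matching the stated 32. The total is 64 × 1.3 = 83.2, rounded up to 84, or 42 per arm. The 30% allowance is 0.30 × 84 = 25.2, about 25 patients.

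**Inputs.** From the documents: 42 per arm, effect 0.35, SD 0.5. Assumed, because the documents give no values: early loss dL (liraglutide) and dP (placebo), all before week 12; a common HbA1c shift c in patients who stay; and the share s of that shift that leavers would have had. Leavers keep no drug effect and behave alike in both arms. The target is the difference at week 26 in all randomised patients, whatever treatment they took. That target is also an assumption, since section 17.1 names none. A reduction favouring liraglutide is positive, and the analysis is unadjusted.

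**Formulas.**
- LOCF difference = (1 − dL)(0.35 + c) − (1 − dP)c
- Target = (1 − dL)(0.35 + c) + dL·s·c − [(1 − dP)c + dP·s·c]
- LOCF minus target = s·c·(dP − dL)

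The bias is zero if early loss is equal, if c = 0, or if s = 0.

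**Worked case.** dL = 0.30, dP = 0.05, c = 0.3 (a fall): LOCF = 0.70 × 0.65 − 0.95 × 0.3 = 0.455 − 0.285 = 0.17. With s = 1 the target is 0.70 × 0.35 = 0.245. The gap is 1 × 0.3 × (0.05 − 0.30) = −0.075.

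| Early loss (liraglutide / placebo) | Common shift | LOCF | Target, s = 1 | Target, s = 0 |
|---|---|---|---|---|
| 30% / 5% | 0.3 fall | 0.17 | 0.245 | 0.17 |
| 30% / 5% | 0.3 rise | 0.32 | 0.245 | 0.32 |
| 20% / 10% | 0.3 fall | 0.25 | 0.28 | 0.25 |
| 30% / 5% | 0.1 fall | 0.22 | 0.245 | 0.22 |
| 20% / 10% | 0.1 fall | 0.27 | 0.28 | 0.27 |

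**Rejection with no drug effect** (simulated t-test, s = 1). At 30% / 5% with a 0.3 fall, LOCF rejects in about 12% of trials: roughly 11.4% favour placebo and 0.3% favour liraglutide. With a 0.3 rise the split reverses. At 20% / 10% with a 0.3 fall it is about 6%, of which about 4.8% favour placebo. If the leavers are measured, the rate is about 5%.

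**Zero spread.** At 30% loss in both arms and no shift, LOCF and target are both 0.245. LOCF variances are 0.7 × 0.25 + 0.7 × 0.3 × 0.35² = 0.201 (liraglutide) and 0.7 × 0.25 = 0.175 (placebo), a pooled SD of 0.433. With leavers measured they are 0.276 and 0.25, a pooled SD of 0.513. Simulated power is about 73% under LOCF and 58% with measured leavers. False positives stay at 5% under LOCF.

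**The case against.** **Leavers may not be wholly unmeasured.** A reader might infer that the plan never measures leavers. The documents do not support that. Section 20.2 allows an end-of-study visit, section 5.3 says most recruits are the centre's own clinic patients, and section 10.4 names medical records as a source, so a clinic HbA1c may exist. What stands is that none is scheduled, timed or committed to the analysis.

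**The size rests on stacked assumptions.** A material bias needs unequal early loss, a sizeable common shift, and leavers who share it. None of these is given in the documents. The preliminary data in section 3.1 report no significant change when optimal insulin control was attempted for at least two weeks. Those were glucose readings in better-controlled patients, so the evidence is weak, but it points towards little shift. The milder cases in the table are indeed small.

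**The rule need not favour the drug.** A reader might take the 12% rejection rate as a raised risk of a false efficacy claim. With falling HbA1c the opposite holds: nearly all those rejections favour placebo. The excess favours liraglutide only if HbA1c rises.

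**Imputation brings its own assumption.** Take 30% / 5% loss, a 0.3 fall and half of leavers measured. Placebo-based imputation gives 0.245 if leavers share the fall, which is correct. If they do not, the observed placebo mean is 0.95 × 0.3 / 0.975 = 0.292, and the estimate is 0.70 × 0.65 + 0.15 × 0.292 − 0.292 = 0.21 against a target of 0.17, where LOCF would be right. This objection stands, so the imputation assumption is the sponsor's choice and a tipping-point analysis is needed whichever is chosen.

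**Conclusion.** The concern holds in a limited form and should be fixed. On the text, every exit before week 12, not only those at weeks 1 and 2, is scored as zero change on the primary endpoint under a literal LOCF, and nothing scheduled can show whether zero is right. In the illustration the error runs from nil to about 0.075 in either direction, against a planned effect of 0.35. It is nil in the unadjusted mean if early loss is equal, if there is no common shift, or if leavers do not shift. The equal-loss result also needs leavers in the two arms to change alike.

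The documents do not support saying that LOCF favours liraglutide, or that the constant zeros by themselves inflate false positives. The zeros do make precision look better than it is: about 73% power against 58% at equal 30% loss with no shift. All of these sizes depend on the assumed loss split, timing and shift. The facts about the schedule do not.

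**What to change.** 1. In sections 10.1, 17.1 and 20.2–20.3, state that patients who stop study drug or are dropped, and who consent, still have HbA1c drawn at weeks 12 and 26, and that these values enter the primary analysis as randomised. No clinical stopping rule changes.
2. Do not let a carried-forward screening value be the only primary handling. For leavers still without a post-baseline HbA1c, use multiple imputation that includes all randomised patients under a pre-specified assumption. Placebo-based imputation is one option; the choice is the sponsor's. Keep LOCF as a sensitivity analysis and state how it treats patients with no post-baseline value.
3. Add a tipping-point analysis on the imputed values.
4. Reconcile the week 4 text of section 10.1 with section 21.1. The first keeps patients with severe nausea or vomiting at the highest dose in the study on a lower dose; the second has patients with severe nausea or vomiting discontinue. The answer decides who becomes a leaver.

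**Cost.** Up to two draws of a test already in the schedule, in up to about 25 patients, or about 15 in the 30% / 5% case (42 × 0.30 + 42 × 0.05 = 14.7). Intervals will be wider. At 30% loss per arm with no shift, power is about 58% if all leavers are measured, and about 51% if half are measured and the rest are placebo-imputed, against the 73% that LOCF appears to give.

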17.2 If applicable, provide a power analysis.

NOTE: This may not apply to certain types of studies, including chart/records reviews, survey studies, or observational studies. This question is asked to elicit whether the investigator has an adequate sample size to achieve the study objectives and justify a conclusion.

Response: There are no prior randomized controlled trials that have examined the effect of Liraglutide on HbA1c in subjects with type 1 diabetes. In our observational study (preliminary data), we found a decrease in HbA1c of 0.35% after 6 months of liraglutide in patients with type 1 diabetes who had a mean HbA1c of $6.45\pm0.5\%$. In our proposed study, we will include patients with HbA1c up to 8.5%. Thus we expect a greater difference in HbA1c among the two groups at the end of the study. Conservatively estimating a difference in HbA1c of 0.35% between the two groups, a sample size of 32 patients per treatment group should provide 80% power to detect a significant difference ($\alpha = 0.05$), provided the standard deviation of the residuals is not greater than 0.5. Thus 64 subjects will be needed for the study. To account for a dropout rate of 30%, we will recruit 84 subjects into the study.

17.3 Describe any procedures that will be used for quality control of collected data.

Response: Three investigators and research nurse will double check the accuracy of collected data. All laboratory testing will be standardized using references and standards.

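### Glycaemic secondary endpoints are compared by a t-test on change without baseline as a covariate, and the other secondaries by an open choice of t-test or ANCOVA, although most baselines are collected

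*Combined protocol and SAP*

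**What the plan says.** Section 17.1 sets three between-arm rules.

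- **Primary endpoint (HbA1c):** ANCOVA at the 0.05 level, with change in weight as the only named covariate.
- **Glycaemic secondaries:** mean weekly glucose, its SD, HbA1c again, fructosamine, time in hyper- and hypoglycaemia, insulin dosage and meal AUC. For these: "Between groups comparisons of the magnitude of change from baseline will also be made for these glycemia related secondary endpoints using student's t-test".
- **Other secondaries**, including fasting and postprandial glucose, glucagon, C-peptide, inflammatory indices, fat mass, blood pressure and questionnaire scores: "Between groups comparisons will be made using students t-test or ANCOVA (adjustment will be done for baseline differences").

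The same section plans a baseline comparison: "The similarities between the study groups, baseline values for subject's demographics and study endpoints will be compared using appropriate parametric tests". It also adds within-arm tests: "Comparisons for these and the primary endpoints will also be made using the paired t-test or Wilcoxon's test for paired data within each group".

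Most of the glycaemic baselines are collected under section 10.1. HbA1c is drawn at screening ("Fasting labs before 10:00am include; CBC, CMP, HbA1c, lipid panel"). Fingerstick and CGM records are gathered before treatment, a meal test is done before treatment, and fructosamine is taken on day 0.

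**The concern.** Two features stand out. First, the glycaemic list gets a two-sample test on change even though the pre-treatment value could enter a model as a covariate. Subtracting the baseline fixes its coefficient at 1. ANCOVA estimates that coefficient and so usually leaves less residual variance.

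Second, the rule for the other secondaries does not say which endpoint gets which test, whether adjustment is always made or only when baselines look different, or what counts as a difference. Because baseline values are to be compared between arms, the observed imbalance could end up choosing the test.

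The two rules also overlap. HbA1c sits under the primary ANCOVA and again under the t-test. Meal AUC falls under the t-test rule, while postprandial glucose from the same meal test falls under the open one. At stake are the width of the secondary confidence intervals in a trial of 84 patients and having one identifiable analysis per endpoint.

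**Working it through.** **The plan's own figure.** Section 17.2 gives 32 per group for 80% power, a difference of 0.35 and a residual SD of 0.5. Taking alpha 0.05 as two-sided: n = 2(1.960 + 0.842)² × 0.5² / 0.35² = 32.04, so 33 after rounding up, and power at 32 is 79.96%. The stated figure reproduces. It concerns HbA1c only; no secondary endpoint has a power statement.

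**Inputs for the comparison.** Allocation is 1:1, 42 per arm (section 4.1). The correlation rho between baseline and week 26 is not in the documents and is assumed at 0.3, 0.5, 0.7 and 0.9.

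**Complete data, equal SDs s.**

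- Variance of a change score: 2(1 − rho)s².
- Residual variance after ANCOVA on baseline: (1 − rho²)s².
- Ratio: (1 − rho²) / [2(1 − rho)] = (1 + rho)/2.
- Saving: (1 − rho)/2.

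At 42 per arm with normal data, estimating the slope multiplies the ANCOVA variance by 1 + 1/(2 × 42 − 4) = 1.0125, which takes off about one percentage point.

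**If dropouts have their baseline carried forward.** With a fraction d carried forward, and dropout unrelated to the values, rho becomes (1 − d)rho + d, so the saving is (1 − d)(1 − rho)/2. Two values of d follow from section 17.2: 64 needed out of 84 recruited gives d = 20/84 = 24%, and the stated rate is 30%.

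| Saving in variance | rho 0.3 | 0.5 | 0.7 | 0.9 |
|---|---|---|---|---|
| Complete data, large sample | 35% | 25% | 15% | 5% |
| Complete data, 42 per arm | 34.2% | 24.1% | 13.9% | 3.8% |
| Baseline carried forward, 24% (large sample) | 26.7% | 19.0% | 11.4% | 3.8% |
| Baseline carried forward, 30% (large sample) | 24.5% | 17.5% | 10.5% | 3.5% |

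**If the SD changes on treatment.** Let the follow-up SD be k times baseline on liraglutide and unchanged on placebo (assumed). Then

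ratio = [1 + k² − rho²(1 + k)²/2] / [3 + k² − 2rho(1 + k)].

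Denominator minus numerator is 2[1 − rho(1 + k)/2]², which is never negative. So with 1:1 allocation ANCOVA is never less precise in large samples. In the pilot's Table 2 the SD of mean weekly glucose falls from 20 to 12, so k = 0.6 and the savings are 48, 41, 35 and 33%. For time below 40 mg/dl the SD rises from 0.2 to 0.3, so k = 1.5 and they are 21, 10, 2 and 4%. The gain therefore differs by endpoint, in both directions from the equal-SD figures.

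**What this means for power.** Suppose an endpoint has 80% power at 32 per arm with the t-test on change. With complete data and equal SDs, ANCOVA has 93.5, 89.9, 86.0 and 82.0% at the four rho values.

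**Type I error**, simulated under no effect with 32 per arm and 40,000 trials per rho:

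| Procedure | Rejection rate |
|---|---|
| t-test on change | 5.0–5.2% |
| ANCOVA only if the baseline test has P < 0.05, otherwise t-test | 4.2–5.1% |
| Smaller of the two P values | 6.2–7.8% |

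**The case against.** The strongest reply is that nothing here is wrong in the sense of invalid. A change score already uses the baseline, by subtraction, and under randomisation its t-test is unbiased and holds its level. For the glycaemic list the test is fixed in advance. The endpoints carry no power claim, and the size of the gain rests on a correlation that the documents do not give. All of that stands. It makes the point minor, but it does not remove a gain that costs almost nothing.

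A reader might infer that the open choice inflates type I error. That happens only if the smaller P value is reported, which the plan does not propose. Letting baseline imbalance decide does not raise the error above 5% beyond simulation noise. A reader might also infer that within-arm tests are to replace the comparison with placebo. Section 2.1 defines the secondary endpoints as change compared with placebo, and 17.1 adds the paired tests alongside, so the text does not support that.

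The carried-forward figures are conditional. The sentence "Analysis will be carried out on the basis of intention to treat (with last observation carried forward") stands in the primary-endpoint paragraph. The plan does not say that it covers the secondaries, or that a pre-treatment value may be carried forward. HbA1c and fructosamine are also measured at week 12, so for them those rows would not apply to patients lost after that visit.

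Skewed endpoints such as time in hypoglycaemia are partly provided for, because 17.1 already allows transformation.

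**Conclusion.** The point holds as a matter of precision and of naming one test, for secondary endpoints only. With complete data and equal SDs, adjusting for the endpoint's own baseline lowers the variance by about 35, 25, 15 or 5% for assumed correlations of 0.3, 0.5, 0.7 or 0.9. If baseline is carried forward for 24 to 30% of patients, the range becomes about 27% down to 3.5%. If the SD changes on treatment, the gain may be larger or smaller. At high correlation it is small in every equal-SD case.

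The documents do not support a claim of bias, of an invalid t-test, of baselines left unused, or of an inflated error rate. The covariate chosen for the primary ANCOVA is a separate matter and is not judged here. Severity: minor; a free improvement.

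**What to change.** In section 17.1, replace the two between-arm rules for secondary endpoints with one:

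> *Each continuous secondary endpoint with a recorded pre-treatment value is compared between arms by a single ANCOVA of its 26-week value on treatment arm and that endpoint's own baseline, whatever imbalance is observed. Skewed endpoints may be transformed, as already provided.*

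Remove HbA1c from the t-test list, since it already has the primary ANCOVA. The one rule then covers both meal AUC and postprandial glucose.

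The cost is wording and one degree of freedom per model. HbA1c and fructosamine need no new measurement.

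Some separate points need settling before the baseline is defined for certain endpoints. Section 10.1 places the baseline meal test at day -7, day -1 and week 0. It asks patients "to wear their CGM constantly for a week" but takes 14 days of records as the glucose baseline. It names no visit for recording insulin dose, SF-36, PHQ or waist circumference. These passages must be reconciled or completed under any analysis of change from baseline.
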